7.8.2 Adverse Event: Definitions

7.8.2.1 Adverse Event

An adverse event is any untoward medical occurrence in a subject or clinical investigation patient administered a pharmaceutical product and which does not necessarily have to have a causal relationship with this treatment. An AE can therefore be any unfavorable and unintended sign (e.g., an abnormal laboratory finding), symptom, or disease temporally associated with the use of a medicinal product, whether or not considered related to the medicinal product.

An adverse event will also be considered to be any untoward effect of a study-related procedure, which is conducted after signed informed consent and prior to study drug administration.

7.8.2.2 Adverse Drug Reaction

Adverse drug reaction (ADR) is a noxious and unintended response to the medicinal product related to any dose. As used herein, the phrase “response to a medicinal product” means that a causal relationship between a medicinal product and an AE is at least a reasonable possibility (i.e., the relationship cannot be ruled out).

7.8.2.3 Adverse Event of Special Interest

An AESI is an event of scientific and medical interest or concern to the Sponsor’s product or program, for which ongoing monitoring and rapid communication to the Sponsor could be appropriate. It may be a serious or non-serious AE, which may require further investigation in order to characterize and understand it.

7.8.2.4 Treatment Emergent Adverse Event

An event that is temporally associated with administration of study product is defined as a treatment-emergent adverse event (TEAE). Events meeting this definition will be those occurring during or after administration of the first dose of study drug. Events that existed before the first administration of study product and then increased in severity during or after the first administration of study product will also be considered treatment emergent. Such

events will be captured on the eCRF as new events, with the onset date as the date of the increase in severity.

7.8.2.5 Serious Adverse Events

A SAE is any adverse event that results in any of the following outcomes:

- Death
- Life-threatening (immediate risk of death)
- Inpatient hospitalization or prolongation of existing hospitalization (even if the event is Grade 1)
- Persistent or significant disability or incapacity
- Congenital anomaly/birth defect
- Important medical events that may not result in death, be life-threatening, or require hospitalization may be considered SAEs when, based upon appropriate medical judgment, they may jeopardize the patient and may require medical or surgical intervention to prevent one of the outcomes listed in this definition. Examples of such medical events include allergic bronchospasm requiring intensive treatment in an emergency room or at home; blood dyscrasias or convulsions that do not result in inpatient hospitalization or the development of drug dependency or drug abuse.

7.8.2.6 Immediately Reportable Event

IREs are events that must be reported immediately to MacroGenics Product Safety within 24 hours of being identified. IREs include but are not limited to:

- SAEs
- AEs leading to permanent discontinuation of study drug in an individual patient.
- Pregnancy in a study patient or partner of a study patient. [Note: If the female partner of a male patient becomes pregnant, the partner must be requested to complete a Pregnant Partner Consent Form so that pregnant partner, fetal and/or newborn information can be collected.]
- The following AESIs ([Section 7.8.3](#)):
 - Grade 3 infusion-related reactions or CRS (see [Section 6.5.1](#))
 - irAE (see [Section 6.5.2](#))
- Administration of a dose significantly greater than the planned dose of either MGA271, pembrolizumab, or MGA012 resulting in an event of clinical consequence.

- Withdrawal of the patient from study drug administration for any reason other than disease progression.
- Abnormal liver enzymes that meet the criteria for potential Hy's law, which is defined as AST and/or ALT that is greater than $3 \times$ ULN and total bilirubin that is greater than $2 \times$ ULN without any alternate etiology

In those cases, in which the IRE is considered related to study drug, the study drug may be discontinued and the patient will continue participation in the study for observational safety and analysis (except for cases where the patient is withdrawn from the study by the Investigator). At any time after completion of the study, if an Investigator becomes aware of a serious adverse event that s/he suspects is related to study drug, the Investigator should report the event to MacroGenics, Inc. Product Safety.

7.8.3 Adverse Events of Special Interest

AESI will include the following:

- Infusion reactions including cytokine release syndrome
- Immune-related AE of Grade 3 or greater suggestive of an autoimmune process, including but not limited to: pneumonitis, colitis, autoimmune hepatitis, arthritis, glomerulonephritis, myocarditis and cardiomyopathy, hypophysitis, thyroiditis, myositis, uveitis, neurotoxicity, or other autoimmune endocrinopathies, pericarditis, or dermatologic toxicity.

7.8.4 Product Quality Issue with Clinical Consequences

If a product quality issue results in an event of clinical consequences, from the use of study product, it must be immediately reported to the Sponsor/designee as an IRE. The Sponsor will collect the information and evaluate accordingly to protect the safety of the study patients.

7.8.5 Performing Adverse Event Assessments

A physician's assessment of the event is expected to be completed in conjunction with reporting an IRE to the MacroGenics Product Safety/designee.

Medical evaluation and classification of the adverse event must be performed by the Investigator who is qualified to review AE information. The determination of seriousness, severity and causality must be made according to the following criteria:

Assessment of Seriousness: Event *seriousness* will be determined according to the definition of an SAE in **Section 7.8.2**. Seriousness serves as a guide for defining regulatory reporting obligations for AEs.

Assessment of Severity: Event *severity* will be assigned according to the Investigator's assessment using the CTCAE Version 4.03 (for described events and syndromes). For events not contained in CTCAE, the Investigator may assign severity according to the following scale:

- Grade 1 = Mild
- Grade 2 = Moderate AE
- Grade 3 = Severe AE
- Grade 4 = Life-threatening or disabling AE
- Grade 5 = Death related to AE

Any event or laboratory value judged as Grade 4 severity should be separately evaluated to determine whether it also meets the serious criterion of "immediately life threatening."

Note: Severity is not synonymous with seriousness. The term "severe" is often used to describe the intensity (severity) of a specific event. The event itself, however, may be of relatively minor medical significance (such as severe headache). This is not the same as "serious," which is based on patient/event outcome or action criteria usually associated with events that pose a threat to a patient's life or functioning.

Assessment of Causality: The Investigator is required to provide an assessment of causality or relationship of AEs to the study drug based on 1) temporal relationship of the event to the administration of study drug; 2) whether an alternative etiology has been identified, and 3) biological plausibility. Causality must be assessed separately for each drug. The causality assessment categories that will be used for this study are described below.

Causality assessments that are considered **not related** to study drug:

None: The event is related to an etiology other than the study drug (the alternative etiology should be documented in the patient's medical record).

Unlikely: The event is unlikely to be related to the study drug and likely to be related to factors other than study drug.

If an SAE is considered "unlikely" or "unrelated" to study drug, the Investigator should offer his/her clinical opinion as to what factor(s), agent(s), or process(es) were the likely causative mechanism for the event.

Causality assessments that are considered **related** to study drug:

Possible: There is an association between the event and the administration of the study drug and there is a plausible mechanism for the event to be related to study drug; but there may also be alternative etiology, such as characteristics of the patient's clinical status or underlying disease.

Probable: There is an association between the event and the administration of study drug, a plausible mechanism for the event to be related to the study drug and the event could not be reasonably explained by known characteristics of the patient's clinical status or an alternative etiology is not apparent.

Definite: There is an association between the event and the administration of study drug; a plausible mechanism for the event to be related to the study drug and causes other than the study drug has been ruled out and/or the event re-appeared on re-exposure to the study drug.

Assessment of Expectedness: As part of the regulatory reporting requirements, the Sponsor must perform an assessment of expectedness (expected/unexpected from the perspective of previously observed, not on the basis of what might be anticipated from the pharmacological properties of a medicinal product) for AEs. Adverse reactions will be considered unexpected if the nature, seriousness, severity or outcome of the reaction(s) is not consistent with the reference information (e.g., the Adverse Drug Reaction section of the Investigator's Brochure) for the study product.

7.8.6 Reporting of Adverse Events to the Sponsor

Adverse events will be collected and followed from the time the patient provides informed consent for the study until the End of Treatment visit or 28 days after the last dose of study drug. If a patient experiences an AE after the informed consent document is signed and prior to treatment with study drug, it should be captured as medical history; however, if the Investigator believes the AE may have been caused by a protocol-related procedure it will be recorded as an AE and entered onto the eCRF.

Adverse events occurring after the patient undergoes early termination or completes the trial (completes the End of Treatment visit), need not be reported unless the event is serious and the Investigator believes that the event may have been caused by the study drug or a protocol procedure.

To identify the occurrence of any new medical complaints or worsening of previous complaints, non-leading questioning should be posed to the patient.

Events related to disease progression/worsening of underlying disease (including those with a fatal outcome) will be collected as efficacy endpoints, and not documented as AEs/SAEs. These events may not qualify for expedited reporting to regulatory agencies if consistent with expected rates of progression for the underlying disease. However, if an SAE occurs in a patient and it is unclear if the event is due to progressive disease, the SAE should be reported.

If a patient reports signs and symptoms that represent a single medical syndrome, diagnosis, or concept, the syndrome/diagnosis/concept should be documented (e.g., cough, runny nose, fever = Upper Respiratory Tract Infection) in the eCRF.

The Investigator must follow all SAEs until resolution and record the date of resolution. Resolution of an event is defined as the return to pre-treatment status or stabilization of the condition with the expectation that it will remain chronic.

Adverse events occurring after the patient completes the trial or after early termination need not be reported unless the event is serious and the Investigator believes that the event may have been caused by the study drug or a protocol procedure.

Clinical Laboratory Changes: Safety laboratory assessments will be carried out locally and evaluated by the Investigator to ensure patient safety. The Investigator is responsible for reviewing the results of all laboratory tests as they become available. Laboratory tests will be graded according to CTCAE v 4.03. Laboratory values that fall outside of a clinically accepted reference range or values that differ significantly from previous values must be evaluated by the Investigator for clinical significance. The Investigator may repeat the laboratory test or request additional tests to verify the results of the original laboratory tests. If the Investigator determines the laboratory value is an abnormal change from baseline and is of clinical significance for that patient, it is considered an AE. Generally, Grade 1 laboratory findings need not be reported as AEs unless clinically significant. The Investigator will evaluate laboratory findings of \geq Grade 2 or higher classification to determine their clinical significance and if an AE has occurred. Consistent with the CTCAE designation of Grade 3 events as severe or medically significant and Grade 4 events as life-threatening, Grade 3 and Grade 4 laboratory findings should be reported as AEs or SAEs, as appropriate. Grade 2 laboratory findings may be reported as AEs if, in the opinion of the Investigator, the event exhibits clinical significance. If clinically relevant abnormal laboratory values are associated with clinical symptom(s), or consistent with a diagnosis, the diagnosis should be reported as the AE (e.g., hemoglobin 9 g/dL in an adult female = anemia). If these clinically relevant abnormal laboratory values do not result in a diagnosis, the test result or finding should be reported as the AE assuming that it does not represent a laboratory error. Repeat testing may be indicated. Such laboratory values should generally be recorded as “increased” or “decreased” (e.g., change from baseline hemoglobin of 13 g/dL to 11 g/dL = hemoglobin decreased).

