- The safety assessment will be based on the evaluation of treatment-emergent AEs that occur from the time of initiation of administration of either study drug through the End of Treatment Visit or 28 days after the last dose of study drug (whichever is later) and will be determined based on signs, symptoms, physical examination findings and/or laboratory test results from enrolled patients as appropriate
- AEs and SAEs will be collected from the time the patient receives the first dose of study drug until the End of Treatment Visit or 28 days after the last dose of study drug (whichever is later). Protocol-related AEs and SAEs will be collected from the time the patient has consented to study participation.
- AEs reported between the time the patient signed the informed consent and the administration of the first dose of study drug will be captured as medical history.
- SAEs considered related to study drug may be reported at any time, even after the patient's final visit.
- Progression of the underlying neoplasm resulting in hospitalization or death (e.g., patient hospitalized for or dies from progressive disease [PD] only, without any other SAE) will be documented as an antitumor activity outcome and not as an SAE. If an SAE occurs in a patient and it is unclear whether the event is related to PD, the SAE should be reported.
- The reporting of laboratory/vital signs abnormalities as both laboratory findings and AEs should be avoided. They should not be reported as AEs unless any one of the following are met:

Any criterion for an SAE is fulfilled

The laboratory/vital signs abnormality causes the patient to discontinue from the study treatment

The laboratory/vital signs abnormality causes the patient to interrupt the study treatment

The laboratory/vital signs abnormality causes the patient to modify the dose of study treatment

The laboratory/vital signs abnormality requires intervention

Efficacy Assessments:

Tumor assessments will be obtained at screening using CT and/or MRI scans at time intervals as specified in the [Appendix 1](#) (Time and Events Table). The study is divided into 6 Tumor Assessment Cycles; the first is

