4.1.4 Efficacy Follow-up Period

The **Efficacy Follow-up Period** consists of the 6-month (24-week) period following the final dose of study drug (pembrolizumab or MGA271 or MGA012, whichever is last) where patients will be followed for survival via telephone or other electronic contact at 12-week intervals from the start of the period. Patients who discontinue study treatment for a reason other than progressive disease may be followed for efficacy and survival until 1 of the following occurs: the patient progresses, withdraws consent for follow up, or initiates other anti-cancer therapy, or the overall trial is closed.

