7.6.2 Sample Collection, Storage, and Shipping

Clinical laboratory testing described in **Section 7.6.1** will be performed locally. Details on local and central laboratory specimen collection, storage, and shipping will be provided in the Laboratory Manual.

7.7 **Electrocardiography**

Twelve-lead electrocardiograms (ECGs) (in triplicate, approximately 1 minute apart) will be obtained according to the ([Appendix 1](#)) in order to evaluate the potential cardiac effects of the combination of MGA271 and pembrolizumab and of MGA271+MGA012, including QT interval. There are no requirements for fasting and no restrictions for fluid and food intake by the patients during the study, although it is recommended that, to the extent possible, ECGs be obtained pre-meal at approximately the same time of the day to minimize diurnal variations. However, this may not be possible because of infusion times and clinic logistics.

To account for intrinsic variability, all ECGs should be obtained in triplicate (3 ECGs per time point at approximately 1-minute intervals). Central interpretation will be used for data analysis purposes; note for Cohort 4 only, ECGs will be read locally. ECGs are to be obtained as specified in [Table 8](#) for MGA271 and pembrolizumab and in [Table 9](#) for MGA271 and MGA012.

7.8 **Safety Assessments**

7.8.1 **Criteria for Evaluation**

- The safety assessment will be based on the evaluation of treatment-emergent AEs that occur from the time of initiation of administration of either study drug through the End of Treatment Visit or 28 days after the last dose of study drug (whichever is later) and will be determined based on signs, symptoms, physical examination findings and/or laboratory test results from enrolled patients as appropriate.
- AEs and SAEs will be collected from the time the patient receives the first dose of study drug until the End of Treatment visit or 28 days after the last dose of study drug (whichever is later). Protocol-related AEs and SAEs will be collected from the time the patient has consented to study participation.
- AEs reported between the time the patient signed the informed consent and the administration of the first dose of study drug will be captured as medical history.
- SAEs considered related to study drug may be reported at any time, even after the patient's final visit.

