8.3 End of Treatment Visit

A list of evaluations to be performed for the End of Treatment visit is provided in [Appendix 1](#). Criteria for triggering the End of Treatment visit are specified in [Section 5.3](#). The End of Treatment Visit should be performed after the patient has met off-study criteria or has been followed for at least 28 days after the last dose of study drug depending on ability to follow the patient and duration and severity of ongoing AEs. It is recognized that certain patients (such as those experiencing progression of disease) may be cared for in facilities other than the participating investigational site, may proceed to receive other cancer therapy, and/or may elect not to return to the investigational site. Therefore, this visit is considered optional, but should be carried out whenever possible.

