5.2 Safety Endpoints

5.2.1 Adverse Events

Adverse event (AE) means any untoward medical occurrence in a patient or clinical trial patient associated with the use of a drug in humans, whether or not considered drug related. An adverse event can therefore be any unfavorable and unintended sign (including an abnormal laboratory finding, for example), symptom, or disease temporally associated with the use of a medicinal product, whether or not considered related to the medicinal product. Only treatment emergent adverse events (TEAEs) will be summarized as safety endpoints. A TEAE is defined as any event that is newly occurring on or after the administration of study drug or an event that existed before but increased in severity on or after study drug administration.

All adverse events whether serious or non-serious, will be reported from the time a signed and dated ICF is obtained through the end of treatment visit (EOTV) or 28 days following the last dose of study (whichever occurs later). These events will be recorded by the Investigators in the electronic case report forms (eCRFs). AEs will be coded using the most recent version of the Medical Dictionary for Regulatory Activities (MedDRA). An assessment of severity grade will be made using National Cancer Institute- Common Terminology Criteria for Adverse Events (NCI-CTCAE) Version 4.03.

Both protocol-related AEs and serious adverse events (SAEs) will be collected from the time the patient has consented to study participation. AEs and SAEs reported between the time the patient signs the ICF and the administration of the first dose of study drug will be captured as concurrent medical history unless the events are attributed to protocol-specified procedures. Events attributed to protocol-specified procedures will be collected on the Adverse Event eCRFs and SAE Report form as appropriate.

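### Protocol 7.8.6 lets adverse-event reporting stop before Day 28 after the last dose, in conflict with the Synopsis, Section 7.8.1 and SAP 5.2.1

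*Protocol*

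**What the plan says.** Three places give the same end of AE collection:

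- Protocol Synopsis, safety assessments: "until the End of Treatment Visit or 28 days after the last dose of study drug (whichever is later").
- Protocol 7.8.1, Criteria for Evaluation: "until the End of Treatment visit or 28 days after the last dose of study drug (whichever is later").
- SAP 5.2.1: "through the end of treatment visit (EOTV) or 28 days following the last dose of study (whichever occurs later").

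Protocol 7.8.6, the section on reporting AEs to the sponsor, differs in two ways. Its opening sentence collects events "until the End of Treatment visit or 28 days after the last dose of study drug", without saying which of the two dates governs. It then states an exemption: "Adverse events occurring after the patient undergoes early termination or completes the trial (completes the End of Treatment visit), need not be reported", and the sentence goes on to keep events that are both serious and possibly caused by study drug or a protocol procedure. A near-identical sentence at the end of the general text repeats the exemption: "need not be reported unless the event is serious and the Investigator believes that the event may have been caused by the study drug". Suspected causation by a protocol procedure is again the alternative.

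Section 8.3 times the End of Treatment visit "after the patient has met off-study criteria or has been followed for at least 28 days after the last dose of study drug", takes its triggers from the discontinuation criteria in Section 5.3, and makes the visit optional. Section 4.5.1 sends patients with a drug-related delay of more than 14 days to that visit and then to efficacy follow-up, with no wait to Day 28.

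**The concern.** When the End of Treatment visit falls before Day 28, a site cannot apply both rules. Section 7.8.1 and the SAP want everything up to Day 28. Section 7.8.6 excuses most of what happens after the visit.

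Safety and tolerability are the primary objectives (Protocol 3.1), and SAP 6.7.1 tabulates only treatment-emergent AEs. If some sites stop at the visit and others go on to Day 28, the incidence tables pool patients with different lengths of off-treatment observation, and the reader cannot tell which patients had which. The later contacts are not designed to recover the gap: in the Efficacy Follow-up Period, "patients will be followed for survival via telephone or other electronic contact at 12-week intervals from the start of the period".

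**Working it through.** There is no sample-size or error-rate figure to reproduce here. The check is a comparison of texts plus a count of days.

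**Step 1. The two windows.** Let v be the day of the End of Treatment visit, counted from the last dose of either drug.

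- Synopsis, 7.8.1 and SAP 5.2.1: collection ends on day max(v, 28).
- 7.8.6 exemption read literally: routine reporting ends on day v.
- Days lost = max(0, 28 − v).

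**Step 2. Can v be below 28?** Yes. The either-or in 8.3 sets no minimum interval on its first branch, and 4.5.1 names no Day 28 wait.

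**Step 3. How large could the gap be?** The documents give no actual visit dates, so the timings below are assumptions applied to the dosing and scan days in Appendix 1 and Tables 8 and 9.

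| Assumed route to the visit | Last dose | Visit | v | Days lost |
|---|---|---|---|---|
| Weekly MGA271, on scan day, Cycle 1 | Day 36 | Day 42 | 6 | 28 − 6 = 22 |
| Weekly MGA271, on scan day, later cycle | Day 57 | Day 63 | 6 | 28 − 6 = 22 |
| Cohort 4, on scan day, Cycle 1 | Day 22 | Day 42 | 20 | 28 − 20 = 8 |
| Cohort 4, on scan day, later cycle | Day 43 | Day 63 | 20 | 28 − 20 = 8 |
| Weekly MGA271, delay just over 14 days from the missed dose | – | – | about 7 + 14 = 21 | about 7 |
| Cohort 4, delay just over 14 days from the missed dose | – | – | about 21 + 14 = 35 | 0 |

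Immediate early termination would take the loss towards the full 28 days.

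**Step 4. Which events fall in the gap?**

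| Event after the visit, before Day 28 | Under 7.8.6 | Other rules |
|---|---|---|
| Non-serious, not of special interest, related or not | Need not be reported | Collected only through 7.8.1, the Synopsis and the SAP |
| Non-serious, immune-related | Need not be reported | Immediately reportable under 7.8.2.6, which states no grade; 7.8.3 defines these as Grade 3 or greater; no end date |
| Serious, judged unrelated | Need not be reported | 7.8.2.6 lists serious AEs without a causality test, and 11.2 requires them regardless of causality; no end date |
| Serious, possibly related | Still reported | 7.8.1 accepts these at any time |

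Only the first row lacks a second reporting route. In the second and third rows, 7.8.6 contradicts further sections of the protocol.

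**Step 5. What cannot be computed.** The documents give no event rate for the days after the last dose and no distribution of v, so no count of missing events follows. The dose-limiting toxicity count is less exposed, because Section 4.3 replaces patients without such a toxicity who are not evaluable for the full evaluation period.

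**The case against.** The strongest reply is that 7.8.6 is loose drafting that other text corrects. The window is stated correctly three times, and the opening sentence of 7.8.6 still names 28 days. Section 7.9 asks for all AEs to be documented throughout the study. Section 8.3 ties the timing of the visit partly to the duration and severity of ongoing AEs. Tables 5 and 6 place the final pharmacokinetic and antibody samples 28 days after the last dose, and Appendix 1 shows those samples in the End of Treatment column, so a visit near Day 28 was probably intended. Much of this stands, and it makes the loss conditional: a site that follows 7.8.1 loses nothing. It does not remove the contradiction, because no text says which section governs and 8.3 does not require the Day 28 visit. For Cohort 4, Appendix 2 gives the End of Treatment samples no specific time point, so that evidence of intent is weaker there.

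A reader might infer more than the documents support, in three ways.

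- *That all AE reporting ends at the visit.* It does not. Serious, possibly related events remain reportable, and Step 4 shows separate rules for unrelated serious AEs and immune-related AEs.
- *That events are lost, and lost selectively in patients who stop for toxicity.* Neither is shown. The gap on the toxicity-delay route is smaller than on the scan-day route. Section 7.8.2.6 also keeps patients with a related immediately reportable event in the study for safety observation, unless the investigator withdraws them.
- *That long drug exposure or late immune toxicity enlarges the problem.* Those facts bear on whether 28 days is long enough, which is a separate question. They do not bear on a conflict inside a 28-day window.

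**Conclusion.** The inconsistency is real, and it touches the data for the primary objectives. A site that follows 7.8.6 as written may omit events that the SAP counts, mainly non-serious AEs that are not of special interest. On the assumption that the visit takes place on the scan day that triggers discontinuation, up to 22 of the 28 days (22/28 = 79%) could go unreported with weekly MGA271, and up to 8 (8/28 = 29%) in Cohort 4. These are upper limits on days of observation under that assumption. They do not estimate missing events.

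Protocol 2.3.1.1.2 says the pembrolizumab cohorts are closed and their patients have completed combination treatment. A change of wording therefore helps mainly Cohort 4, which is capped at 15 patients per dose level and has the smaller scan-day gap. For the earlier patients, the open question is which cut-off was actually used.

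**What to change.** 1. In Protocol 7.8.6, add *whichever is later* to the opening sentence, and limit both exemption sentences to events after that later date.
2. In 8.3 or 7.8.6, state that AEs are queried at Day 28 after the last dose, for example by telephone, when the End of Treatment visit is earlier or not done.
3. State that 7.8.6 does not narrow the requirements in 7.8.2.6, 7.8.3 and 11.2 for serious and immune-related events.
4. For the completed pembrolizumab cohorts, report which cut-off sites applied. Comparing each patient's End of Treatment date with the last dose date would show how many had a visit before Day 28.

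SAP 5.2.1 needs no change to its window. The cost is a few sentences of protocol text, one AE query per Cohort 4 patient with an early or missing visit, and one descriptive summary in the study report.
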